## 7.2 Alert format

An example of an alert is shown in Figure 2. The alert education information is customized to the provider based on their patient's clinical characteristics such as 1) the specific reasons that the patient is eligible for a statin (for example, ASCVD risk score or other diagnoses), 2) whether a moderate or high-intensity statin is recommended, 3) whether the patient has liver disease, and 4) whether the patient may have familial hypercholesterolemia based on their cholesterol level. The alert also displays liver testing results for the patient and provides options for statin medications to prescribe. One statin prescription is defaulted, such that if the provider accepts the reminder, the statin medication will be prepared for signing. The clinician also has the opportunity to choose a different statin or a referral to a specialist such as a lipid or gastroenterology specialist. If the clinician does not wish to prescribe a statin at this time, they may select an "acknowledge reason" which specifies the reason for declining statin prescription. The alert also has a feedback link where the clinician can provide feedback about the alert.

The text and information displayed in the alert will remain identical whether the provider receives the interruptive reminder or the non-interruptive alert. The only way that the alert will differ between interruptive and non-interruptive arms is the place in the workflow in which the clinician encounters it.

Study Protocol. Version August 9, 2024  
Full Study Title: Interruptive versus Non-Interruptive Reminders for Statin Therapy in Primary Care (INIRSHA-PC). A Randomized Trial.  
Primary Investigator: [name], MS

! Statin therapy recommended

Patient is recommended to be on **moderate intensity statin** for the following reason(s):  
• Patient may have an ASCVD risk score  $\geq 10$

Here are the patient's most recent LFTs:

Component	Value	Date
ALT	22	05/16/2022
AST	27	05/16/2022
ALKPHOS	97	05/16/2022
BILITOTAL	0.7	05/16/2022

If the patient has a history of statin intolerance and you're unsure of whether to start a statin, consider reviewing [UpToDate](#) or placing a referral to the lipid clinic.

Order	Do Not Order
Order	Atorvastatin (LIPITOR) tablet 20 mg
Order	Rosuvastatin (CRESTOR) tablet 10 mg
Order	Ambulatory referral to lipid clinic

Acknowledge Reason

Statin is not indicated  Statin is contraindicated  History of statin intolerance  Not within goals of care  Patient refused  
 Snooze 24 hours  
 Accept (1)

Figure 2. Example of a reminder recommending statin therapy

### 7.3 Interruptive Reminder

Interruptive reminders will be displayed to providers as pop-up alerts at the time of opening the patient chart. These alerts need to be resolved (either through accepting or acknowledging the alert) before the clinician can proceed with interacting with the rest of the patient's chart.

### 7.4 Non-Interruptive Reminder

Non-interruptive reminders will be available on-demand if the clinician prefers to seek them out. To look for a non-interruptive reminder, the clinician must click on the "Plan" section of the patient's chart and select "BestPractice" to open the BestPractice Advisory (BPA) navigator, which shows a list of all the reminders the patient is eligible for (Figure 3). This section will be highlighted in yellow if the patient has reminders for review. Depending on the number of other reminders the patient is eligible for, the clinician may need to scroll down to see the statin reminder.

Study Protocol. Version August 9, 2024

Full Study Title: Interruptive versus Non-Interruptive Reminders for Statin Therapy in Primary Care (INIRSHA-PC). A Randomized Trial.

Primary Investigator: [name], MS

[figure not shown]

Figure 3. Example of a Non-Interruptive Alert Recommending Statin. This alert is shown within a test patient's chart. The clinician must select the "Plan" tab and then click on the "BestPractice" Navigator to see a list of on-demand reminders. Depending on the number of other non-interruptive reminders the patient is eligible for, the clinician may need to scroll through other reminders to find the statin reminder.

## 7.5 Control Group

For patients who are randomized to the control (routine care) arm, the system will record that the patient's provider was eligible for an alert. This will be done by triggering a "silent" alert which is not displayed to the clinician. This "silent alert" exists for data collection purposes. No alert recommending a statin will be displayed to the clinician, either in an interruptive or non-interruptive format.

## 7.6 Duration of the Intervention

As the randomization is anchored to the provider's patient, the provider will receive the same educational intervention for a given patient throughout the course of the study. For interruptive and non-interruptive alert arms, clinicians may or may not still be eligible for a repeat alert depending on how they interacted with the initial alert. If the patient is on a statin, the clinician will not be shown a repeat alert. If the clinician did not prescribe a statin and chose an acknowledgement reason such as "statin is contraindicated", the alert will not be shown again. If the clinician simply closed or "canceled" the alert during the first visit, or if the clinician did not interact with a non-interruptive alert, the alert will be displayed again at the next visit.

Study Protocol. Version August 9, 2024

Full Study Title: Interruption versus Non-Interruption Reminders for Statin tHerApy in Primary Care (INIRSHA-PC). A Randomized Trial.

Primary Investigator: [name], MS

Any alert shown will be customized according to the patient's current clinical characteristics. For example, if the dose intensity indicated for the patient has changed, the reminder will display the currently recommended dose intensity.

## 7. 6 Blinding:

It would be impractical to pursue blinding for the study since the format of the alert is obvious when the alert is displayed. Given the nature of the study intervention, clinicians and investigators will not be blinded to group assignment.

# 8.0 Data Collection:

## 8.1 Outcomes:

**Primary Effectiveness Outcome:** The primary outcome is statin prescription within 24 hours of BPA firing.

This outcome will be measured within the first 24 hours after the interruptive, non-interruptive, or silent BPA is fired. Only prescriptions for statins which are signed by the provider, and not canceled, will be included in this measurement.

### **Justification for the Primary Effectiveness Outcome**

The primary purpose of the reminder is to encourage statin prescription. Most prescribing as a result of the reminder is likely to occur within the first 24 hours after the alert.

### **Secondary Effectiveness Outcome:**

The secondary outcomes are statin prescription within 12 months post-intervention, and the first post-intervention LDL-C level.

### **Exploratory Outcomes:**

The exploratory outcomes are any non-statin lipid lowering agent prescription within 12 months post enrollment BPA firing, any statin prescription filled within 12 months of enrollment BPA firing, any new ASCVD event occurrence within 12 months of enrollment BPA firing, and time from enrollment BPA firing to statin prescription.

## 8.2 Baseline data:

Age, sex, height, weight, body mass index, race, ethnicity, active medical problems at the time of visit, active comorbidities, comorbidities contraindicating statin prescription (such as rhabdomyolysis, decompensated liver disease, active dialysis statin intolerance), pregnancy or lactation status, palliative care, ASCVD risk score, ASCVD diagnoses, diabetes, LDL-C, liver function tests (AST, ALT, alkaline phosphatase, bilirubin), glomerular filtration rate, orders for coronary calcium CT, status of current visit (acute or routine).

Study Protocol. Version August 9, 2024

Full Study Title: Interruption versus Non-Interruption Reminders for Statin tHerApy in Primary Care (INIRSHA-PC). A Randomized Trial.

Primary Investigator: [name], MS

### 8.3 Data from enrollment to study end:

LDL-C, liver function tests (AST, ALT, alkaline phosphatase, bilirubin.) Date of visits to primary care, hepatology clinic, or lipid clinic. Record of statin reminder, including whether it is displayed, trigger for display, date and time, number of times displayed, role of clinician to whom it is displayed, whether reminder is accepted, acknowledgement reason selected if applicable, free-text comment if applicable. Date, time, and dose of prescription of lipid lowering agent such as statin, ezetimibe, bempedoic acid, PCSK9 inhibitor. Presence of prior statin prescription. Visit type (in person or telemedicine).

### 8.4 Outcome Data:

Primary Outcome: All statin prescriptions signed in the first 24 hours after intervention.

Secondary Outcome: All statin prescriptions signed in the first 365 days after intervention. All LDL-C values resulting from samples collected after intervention and during study period.

Exploratory Outcome: Ezetimibe, PCSK9 inhibitor, or bempedoic acid prescriptions signed in the first 365 days after the intervention. Filling of statin prescriptions within 365 days after the intervention. New ASCVD events recorded within 365 days after the intervention. Date and time of statin prescription signing within 365 days after the intervention.

## 9.0 Risks and Benefits

Lipid-lowering therapy with statins has been shown to reduce relative cardiovascular disease risk by approximately 30 percent. Thus, statin therapy in eligible patients is standard of care to reduce ASCVD risk, and multiple guidelines recommend statin therapy in eligible patients. While adverse reactions such as adverse muscle events and hepatic dysfunction are possible with statin therapy, randomized trials have shown only a slight increased risk of side effects with statin therapy as compared with placebo, and no increased risk of discontinuing therapy. The study intervention is a reminder to clinicians to prescribe guideline-based care. BPAs are not new technology and are encountered on a daily basis by providers. Thus, there is no reason to believe that participation in this study would expose providers or patients to greater risk than those experienced as a part of routine care. This study has a greater benefit to society in the form of improved understanding of how to increase the following of guideline recommendations with EHR interventions.

A potential risk to patients participating in this study involves the collection of protected health information (PHI). In order to limit the associated risks, the minimum amount of PHI necessary for study conduct will be collected. After collection, the data will be stored in a secure, password-protected database only accessible by the investigators. After publication, a de-identified database will be generated to protect participant privacy.

#### Adverse Event Reporting and Communication.

A system has been established to report and track interactions with the EHR-based reminder. Study personnel will monitor the integrity of data confidentiality to protect the safety of subjects and follow any breaches in confidentiality until the event resolves or is explained. Any loss of privacy will be recorded in the AE case report form in the electronic database and reported to the PI within 3 days of occurrence. The PI will report all reportable events to the IRB within 7 calendar days from the PI's knowledge of the event.

## 11.0 Study Withdrawal/Discontinuation

Because this intervention is targeting providers, does not force changes in clinical practice, and has no direct interaction with patients, patients will generally not have the option to self-withdraw from the study.

## 12.0 Statistical Considerations

### **Study Design and Sample Size Consideration**

If we assume that the statin prescribing rate for the control arm (i.e., routine care, or “silent” alert) is 3%, an estimate derived from current clinical data, and the statin prescribing rate for the interruptive statin reminder arm is 6%, a total of 3,006 patients (1,002 patients per arm) would provide 90% power to detect the difference in the statin prescribing rates between the two arms at a type I error rate of 0.05. With a conventional study design, our planned sample size could be a total of 3,000 patients (1,000 patients per arm).

However, considering that this study is a 3-arm trial with substantial uncertainty on the effect size for both the interruptive statin reminder arm and the non-interruptive statin reminder arm, we designed an adaptive clinical trial with sample size adaptation. When sample size reaches 2,250 patients (750 patients per arm), we will conduct an interim analysis to re-estimate the sample size. At the interim, we will calculate the conditional power and re-estimate the sample size that will provide sufficient power. Should the interim analysis confirm that the originally

Study Protocol. Version August 9, 2024

Full Study Title: Interruptive versus Non-Interruptive Reminders for Statin Therapy in Primary Care (INIRSHA-PC). A Randomized Trial.

Primary Investigator: [name], MS

planned sample size of 3,000 patients (1,000 patients per arm) is sufficient, we will proceed without further adjustment and stop recruiting patients when the sample size reaches 3,000 patients (1,000 patients per arm) or the stopping decision is made, whichever occurs later. However, if the interim analysis indicates the need for an increased sample size, we will adjust accordingly based on the re-estimated sample size with the constraint of the maximum sample size of a total of 6,000 patients (2,000 patients per arm).

### **Baseline Characteristics**

To assess randomization success, we will summarize the distribution of baseline variables across the study arms. Categorical variables will be reported as frequencies and proportions while continuous variables will be summarized as mean with standard deviations (SD) or median with range and interquartile ranges (IQR). Variables reported will be specified in a formal Statistical Analysis Plan (SAP).

### **Primary Effectiveness Outcome Analysis**

The primary outcome is a binary outcome of statin prescription at 24 hours post-randomization. To compare the primary outcome between the interruptive reminder arm, non-interruptive reminder arm, and control arm, a logistic regression will be performed with indicator variables for randomized group without adjusting for any other covariates. An overall test regarding whether at least one arm is different from other arms will be performed. If the overall test is significant at the level of 0.05, then additional test will be performed to determine which arm(s) are different compared to the control arm. The analysis set for the primary outcome will be described in the SAP.

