**Primary Aim:**

- To compare the effect of delivering education via interruptive or non-interruptive reminders versus routine care (i.e., fully unprompted) on statin prescribing in primary care clinics within the first 24 hours of alert firing.

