**Primary Hypothesis:**

- Interruptive reminders to providers will be more effective at increasing statin prescriptions within 24 hours of alert firing compared to routine care. Non-interruptive reminders will have no effect on statin prescription rate within 24 hours of firing compared to routine care.

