### 3.0 Rationale, Aims, and Hypotheses

In order to determine the effect of interruptive reminders, compared to non-interruptive reminders, on the rate of statins prescribed in primary care clinics, a randomized trial is needed.

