#### **Study Aims:**

- Primary:
  - o To compare the effect of interruptive versus non-interruptive reminders on statin prescribing in primary care clinics within the first 24 hours of BPA firing.
- Secondary:
  - o To compare the effect of interruptive versus non-interruptive reminders on statin prescribing in primary care clinics within a year after BPA firing.
  - o To compare the effect of interruptive versus non-interruptive reminders on patients' first post-intervention LDL-C level.
- Exploratory:
  - o To compare the effect of interruptive versus non-interruptive reminders on any non-statin lipid lowering agent prescribing within a year after BPA firing.
  - o To compare the effect of interruptive versus non-interruptive reminders on statin prescription filling within a year after BPA firing.
  - o To compare the effect of interruptive versus non-interruptive reminders on incidence of new ASCVD events within a year of BPA firing.
  - o To compare the effect of interruptive versus non-interruptive reminders on the time from BPA firing to statin prescribing.

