#### **Study Hypotheses**

- Principal Hypothesis:
  - o Interruptive alerts to providers will lead to a significant increase in statin prescriptions within 24 hours of BPA firing as compared to no alert.
- Ancillary Hypothesis
  - o Non-interruptive alerts will not lead to a significant increase in statin prescriptions within 24 hours of BPA firing as compared to no alert.

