### 4.0 Study Description

In order to address the aims outlined above, we propose a pragmatic randomized controlled trial evaluating the impact of interruptive versus non-interruptive reminders recommending

Study Protocol. Version August 9, 2024

Full Study Title: Interruption versus Non-Interruption Reminders for Statins tHerapy in Primary Care (INIRSHA-PC). A Randomized Trial.

Primary Investigator: [name], MS

statin prescriptions during primary care visits. All primary care providers caring for patients who are eligible for statin prescribing as defined herein will be included in this study. In the control arm, providers will not receive any additional education beyond what is normally provided.

Providers in the interruptive alert arm will receive additional statin prescribing education via a pop-up reminder that will be automated and displayed to the provider in the moment. Providers in the non-interruptive alert arm will be able to access the same supplementary education via an on-demand reminder within the BPA section of the medical record should they choose to seek this out. Arm assignment will be based on 1:1:1 randomization ratio anchored to the patient's record. Randomization, group assignment and delivery of the intervention will occur within the electronic health record (details in section 7). Data will be collected prospectively from the medical record to determine the effect of the assigned interventions on provider behavior via clinical and physiologic outcomes, such as statin prescriptions and cholesterol levels.

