
With the widespread use of EHRs and the implementation of reminders, the decision to build an alert as interruptive or non-interruptive is an important one which must balance potential alert fatigue with potential positive effects on adherence to clinical guidelines which improve quality of care for patients. Rigorous studies are needed to gather evidence to help clinical informaticians when making decisions about the design of CDS interventions. Findings from such studies would have implications for the thousands of alerts displayed to clinicians each year. To address this knowledge gap, we will conduct a prospective, randomized trial of reminders delivered to clinicians seeing patients in primary care clinics, comparing interruptive vs. non-interruptive reminders in outcomes of statin prescriptions.

Population and Design Considerations

Study Population:

Adult patients (age \geq 18 and < 75) who are treated by primary care providers at Vanderbilt University Medical Center and eligible for statin therapy but not currently on a statin are potentially eligible for this study. If a patient presents to a VUMC primary care clinic and meets the below inclusion and exclusion criteria, the patient will be enrolled to the study.

Inclusion Criteria

- 1. Patients age \geq 18 and < 75
- 2. Seen in primary care visit within Vanderbilt University Medical Center

PI: [name], MS

3. Eligible for statin therapy due to: 1) ASCVD 10-year risk \geq 10%, 2) Type 1 or 2 diabetes and age \geq 40, or 3) ASCVD diagnosis.

Exclusion Criteria

Patient records within the EMR indicate:

- 1. Already on statin, ezetimibe, bempedoic acid, or PCSK9 inhibitor
- 2. Last known LDL-C level < 100 mg/dL
- 3. Known to be pregnant or lactating
- 4. Palliative care
- 5. Statin allergy or adverse effect of statin
- 6. Rhabdomyolysis
- 7. Statin contraindicated due to liver disease, defined as 1) Decompensated liver disease, 2) AST or ALT >5 times the upper limit of normal, or 3) Total bilirubin > 1.5 mg/dL.
- 8. Statin contraindicated due to kidney disease, defined as 1) Dialysis or 2) Estimated glomerular filtration rate < 15 ml/min/1.73 m².
- 9. Has had coronary calcium computerized tomography
- 10. Less than 3 months since lipid panel resulted
- 11. Acute visit

Study Design

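### The primary aim is stated two ways; the final analysis does not list interruptive versus non-interruptive for the primary endpoint, and the protocol and SAP give different testing rules

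*Protocol*

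**What the plan says.** **The aim.** The Primary Aim in protocol section 1.0 compares "interruptive or non-interruptive reminders versus routine care (i.e., fully unprompted) on statin prescribing". The primary entry under Study Aims in section 3.0 reads "To compare the effect of interruptive versus non-interruptive reminders on statin prescribing in primary care clinics within the first 24 hours of BPA firing". Both are current text.

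**Text that leans towards section 3.0's aim.** The rationale opening section 3.0 ("In order to determine the effect of interruptive reminders, compared to non-interruptive reminders, on the rate of statins prescribed in primary care clinics"), section 4.0 ("evaluating the impact of interruptive versus non-interruptive reminders") and the SAP's opening text ("comparing interruptive vs. non-interruptive reminders in outcomes of statin prescriptions").

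**Text that matches section 1.0's aim.** The principal hypothesis in section 3.0 ("Interruptive alerts to providers will lead to a significant increase in statin prescriptions within 24 hours of BPA firing as compared to no alert"), the ancillary hypothesis on the non-interruptive alert, and the sample size in section 12.0 and the SAP, which is for interruptive against control.

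**The final analysis.** Protocol section 12.0, Primary Effectiveness Outcome Analysis, fits a logistic regression with arm indicators and tests for any difference among the three arms at 0.05. If that is significant, "additional test will be performed to determine which arm(s) are different compared to the control arm". The SAP's Primary Analysis uses the same model but lists no pairs, mentions no overall test, and says that it will not adjust for multiplicity. Its Population-Level Summaries section names all three pairs for LDL-C; for binary outcomes it specifies odds ratios without naming pairs.

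**The interim.** Section 12.0 computes conditional power on the prescribing rates for all three pairs.

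**The concern.** Two questions are left open.

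First, which comparison is primary? If it is section 3.0's, the follow-up tests in section 12.0 do not include it, because they are confined to comparisons with control. The reminder-against-reminder difference can then help to set the sample size at the interim yet have no listed pairwise test at the end. The trial's title question would rest on a contrast chosen after the fact.

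Second, when may a control comparison be called significant? Under the protocol, only after a significant overall test. Under the SAP as written, that condition does not appear. The same data can therefore yield a significant control comparison under one document and not under the other.

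**Working it through.** **1. Inputs.** Control 3%, interruptive 6%, 90% power, type I error 0.05, 1,002 per arm (section 12.0 and SAP). Non-interruptive rate anywhere from 3% to 6% (section 12.0 simulations); 4.5% is the midpoint and is my assumption. Sidedness is not stated.

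**2. The plan's own figure.** For two proportions, pooled variance, two-sided:

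n = [1.960·√(2p̄(1−p̄)) + 1.282·√(p₁(1−p₁)+p₂(1−p₂))]² / (p₂−p₁)²

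With p₁ = 0.03, p₂ = 0.06, p̄ = 0.045: [1.960·√0.08595 + 1.282·√0.0855]² / 0.0009 = 1,002 per arm, or 3,006 in total. This matches exactly, so the plan is powered for a single two-sided test of interruptive against control, with no overall test in front of it.

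**3. The direct contrast.** The same formula at 4.5% against 6% gives 4,644 per arm for 90% power, above the cap of 2,000 per arm. At 3% against 6% it is again 1,002.

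**4. Effect of the overall test.** Simulation with 400,000 replicates per scenario. Pairwise tests are pooled z-tests at two-sided 0.05. The overall test is Q = n·Σ(p̂ₖ − p̄)² / [p̄(1−p̄)] on 2 degrees of freedom at 0.05. The adaptive runs place the interim at 750 per arm and compute conditional power for 1,000 per arm from the observed rates. They go to 2,000 per arm unless all three conditional powers are below 50% or at least two exceed 90%. The conditional-power form and this reading of the increase rule are assumptions.

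Chance of any false positive, all arms at 3%:

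| Tests | Rule | 1,000 per arm | Adaptive |
|---|---|---|---|
| Two against control | overall test first | 4.1% | 3.1% |
| Two against control | no overall test | 9% | 6.7% |
| All three pairs | overall test first | 5.0% | 3.7% |

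**5. How often the two documents would disagree.** At 3%/4.5%/6% (control/non-interruptive/interruptive) and 1,000 per arm, at least one control comparison is significant in 91.7% of trials without the overall test and 83.7% with it. The difference, 91.7 − 83.7 = 8 percentage points, is the share of trials in which a control test is significant while the overall test is not. Under the adaptive rule it is about 3%.

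**6. Power with the overall test in place.**

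| Contrast and rates | 1,000 per arm | Adaptive |
|---|---|---|
| Interruptive vs control, 3%/4.5%/6%, no overall test | 91% | 94% |
| Same, overall test first | 83% | about 92% (91.4% in a repeat simulation) |
| Interruptive vs non-interruptive at 4.5%, overall test first | 32% | 48% |
| Interruptive vs non-interruptive at 3%, overall test first | 89% | 96% |

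**7. Why adding the third pair is safe behind the overall test.** With three arms, once any two differ, at most one of the three pairwise null hypotheses can be true, so testing each pair at 0.05 after the overall test does not inflate the error. In simulation the one remaining true null is rejected in about 5% of trials, both when the two reminders are equal at 6% and when non-interruptive equals control at 3%.

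**The case against.** The strongest reply is that the contrast is already there. Section 3.0 names it as the aim, the interim uses it, the overall test is sensitive to it, and the SAP model compares the arms and can produce its odds ratio with a 95% confidence interval. This stands. A reader might infer that the plan never examines reminder format or has excluded the comparison; the documents do not support that. What remains is narrower: no final-analysis section lists the contrast for the primary endpoint, while the SAP does list it for LDL-C.

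A reader might also infer that a format effect will be claimed because one reminder is significant against control and the other is not. No section says so. Likewise, "Non-interruptive reminders will have no effect on statin prescription rate within 24 hours of firing compared to routine care" is a hypothesis, not a statement that a non-significant result will be read as proof of no effect.

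On the testing rule, the SAP's silence does not expressly revoke the protocol's overall test, and the SAP sets no rule for declaring success. That is fair, but a reader following the SAP alone would not apply the overall test. Running all three pairs without it would raise the false-positive rate to about 12% at 1,000 per arm; no section specifies that, so the figure is not held against the plan.

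Finally, keeping the overall test costs power for the principal hypothesis. That is correct and should be stated openly.

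**Conclusion.** The point holds as a gap in specification. The primary aim has two versions. The hypotheses, sample size and follow-up tests agree with section 1.0, so the control comparisons are coherent and the trial is not invalidated. If section 3.0's version stands, its aim has no prespecified pairwise test.

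The difference in testing rule is material but moderate: it roughly doubles the false-positive rate for the two control comparisons when no arm has an effect. At a non-interruptive rate of 4.5%, it leaves the documents disagreeing in about 8% of trials at 1,000 per arm and 3% adaptively. The textual discrepancies need no assumption. The null error rates assume 3% in every arm, the disagreement rates depend on the assumed 4.5%, and the adaptive figures also depend on the conditional-power form used.

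**What to change.** 1. Reconcile the primary aim between protocol sections 1.0 and 3.0.
2. In section 12.0 and in the SAP, list interruptive versus non-interruptive for the primary endpoint beside the two control contrasts, with an odds ratio and 95% confidence interval, tested at 0.05 only if the overall test is significant. Make it primary if section 3.0's aim stands, otherwise supportive. Base any statement about alert format on it.
3. State one testing rule in both documents. Keeping the protocol's overall test ahead of all three pairs holds family-wise error at about 5% or less.

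**Cost.** Text changes only; no patients. Two downsides should be written into the plan. The overall test takes interruptive against control below the planned 90% at a fixed 1,000 per arm when non-interruptive is 4.5%, though not under the adaptive rule. The direct contrast is well powered only if the non-interruptive reminder does little, so a result between the two reminders may be inconclusive.
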